8.1 STATISTICAL CONSIDERATIONS

8.2 Study design and sample size justifications

This randomized phase 2 trial focuses on the definitive primary endpoint of oral cancer-free survival, thus eliminating the limitations of utilizing intermediate endpoints for efficacy analysis. Unfortunately, clinical and/or histologic responses of IEN lesions to chemoprevention interventions only marginally correlate with long-term oral cancer-free survival, as demonstrated by larger-scale retinoid-based therapy trials. As such, the most appropriate way to accurately estimate activity of a candidate drug to manage oral IEN is to use oral cancer-free survival as an endpoint.

The advantages of selecting a molecularly-defined high risk group as the eligible population include: (1) increased number of expected events, thus reducing the sample size; (2) avoidance of exposure of low-risk individuals to the drug, who are unlikely to develop oral cancer and therefore, unlikely to benefit from prevention interventions; (3) improvement of benefit/risk rations and benefit/cost ratios, justifying further use of the drug if positive effects are identified.

The proposed study will be an open-label, observation-controlled randomized study to evaluate the effect of pembrolizumab in a high-risk group of oral IEN patients. There will be two categories of high-risk patients in this study: (a) loss of heterozygosity (LOH) at 3p14 and/or 9p21 in the oral IEN of patients with a history of curatively treated oral cancer and (b) LOH at 3p14 and/or 9p21 plus at one other chromosomal region in the IEN of patients with no oral cancer history.

Study Duration: The trial period is 7 years with 4 years of accrual and 3 additional years of follow-up after last patient's enrollment.

Study Endpoints: The primary endpoint is oral cancer-free survival in patients receiving pembrolizumab as compared with the observation group. Multiple secondary and/or exploratory endpoints will be assessed as outlined in Section 3.2 and 3.3.

Treatment Groups: This is a 2-arm open-label Phase II single-center trial of pembrolizumab versus observation in patients with oral IEN. The trial will randomize 104 patients (1:1)to receive pembrolizumab versus observation.

Sample Size Justification

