The planned sample size is 104 patients. In the recently completed EPOC study, 5.7 patients per month were screened for LOH high risk profiles, 68% were LOH positive, and 59% of the LOH positive patients agreed to be randomized. That study had similar eligibility criteria as proposed herein. As such, we anticipate that for this trial, 250 patients will be screened over 4 years to achieve a total of 104 patients randomized. Sample size calculation was made on the basis of the primary endpoint of the study, time from randomization to onset of oral cancer or death.

Proprietary Information of MD Anderson Document Product: JMK12475, 2016 NCT02882282

Details of the assumptions used for the sample size calculation are listed below.

- 1. The study has a 4-year period to accrue 56 oral IEN/prior cancer and 48 IEN-alone patients, with an additional 3 years of follow-up after last patient is enrolled. The total study duration is 7 years.
- 2. The anticipated yield of LOH screening (described earlier) will be approximately 68%. Assuming an accrual rate of 59% eligible patients, we will need to screen a total of 250 oral IEN patients in order to reach our total accrual goal.
- 3. Time-to-oral cancer development follows an exponential distribution. Based on the data described earlier, 21% of the patients with IEN/LOH associated with curatively treated oral cancer will develop oral cancer in two years, and 15% of the IEN/LOH-alone patients will develop oral cancer in two years.
- 4. Pembrolizumab, the active treatment, can reduce the 2-year oral cancer rate by 52% for the IEN/LOH-cancer history group, i.e., 2-year cancer rate will be reduced from 21% to 10%. This corresponds to a hazard ratio of 0.45. We assume the same treatment effect (hazard ratio) in the IEN/LOH-alone group, corresponding to the 2-year oral cancer rate reduction from 15% to 7%. The parameters, lambda, for the exponential distributions are 0.1179 (control) and 0.053 (treatment) in IEN/LOH-cancer history patients and 0.0813 (control) and 0.0366 (treatment) in IEN/LOH-alone patients, respectively.
- 5. We assume the rate of lost-to-follow up, which includes patient refusal, early drop out, or competing risk, etc. is 10%. The distribution of the time to loss to follow-up is assumed to be uniform.
- 6. Stratified log-rank test is used to compare the cancer-free survival between the active and control groups.

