- 7. One interim analysis is planned at the end of year 3. The final analysis will be performed at the end of the study (year 7). We will apply the group sequential design with the O'Brien-Fleming boundary to control the overall one-sided type I error rate to 10%. The stopping boundaries, i.e. Standardized Z Scale, are 1.899 at the interim analysis and 1.343 at the final analysis

Based on the above assumptions, we ran simulation studies with 10,000 replications. The results show that a total of 104 patients will allow us to have 79% power with a one-sided 10% type I error rate. The study will have 88% power to detect a hazard ratio of 0.4.

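### The stated 88% power at a hazard ratio of 0.40 is not reproduced: the assumptions that give the plan's 79% at 0.45 give about 85 to 86% at 0.40

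*Combined protocol and SAP*

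**What the plan says.** The sample size justification in section 8.2 gives seven numbered assumptions and then two results.

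- Size and accrual: "The trial will randomize 104 patients (1:1)to receive pembrolizumab versus observation"; "The study has a 4-year period to accrue 56 oral IEN/prior cancer and 48 IEN-alone patients", followed by three further years of follow-up.
- Event times: exponential, with yearly hazards of 0.1179 (control) and 0.053 (treatment) in the prior-cancer stratum, and 0.0813 and 0.0366 in the IEN-alone stratum. The design hazard ratio is 0.45 in both.
- Loss to follow-up: 10%, with uniformly distributed loss times. The window is not given.
- Test: stratified log-rank.
- Looks: "One interim analysis is planned at the end of year 3", with the final analysis at year 7. "The stopping boundaries, i.e. Standardized Z Scale, are 1.899 at the interim analysis and 1.343 at the final analysis".

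The results come from 10,000 simulated trials. The first is "79% power with a one-sided 10% type I error rate" with 104 patients. The second is "The study will have 88% power to detect a hazard ratio of 0.4". No separate assumptions are listed for the second.

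**The concern.** The two figures are presented as results of one simulation that differ only in the hazard ratio. They should therefore be reproducible together, and a step from 0.45 to 0.40 should add a predictable amount of power. The printed pair implies a gain of 9 points, which is large for about 29 events.

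The 88% is an operating characteristic of the primary analysis. A reader weighing a null result would use it to judge how likely the trial was to miss an effect of that size. The stated risk is 12%; the listed design implies about 14 to 15%.

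**Working it through.** **Inputs.** All come from section 8.2 except two. Accrual is taken as uniform over the four years, because no pattern is given. The loss window is varied, because it is not stated. Allocation is 28+28 in the prior-cancer stratum and 24+24 in the IEN-alone stratum. Each trial rejects if Z > 1.899 at year 3 or Z > 1.343 at year 7.

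**Hazards.** 0.45 × 0.1179 = 0.0531 and 0.45 × 0.0813 = 0.0366, matching the printed treatment hazards. The simulation therefore appears to have worked from exact hazard ratios rather than rounded 2-year rates. At 0.40 the treatment hazards are 0.0472 and 0.0325.

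**Expected events at year 7, before losses.** With follow-up uniform on 3 to 7 years, P(event) = 1 − [exp(−3λ) − exp(−7λ)]/(4λ). In the order prior-cancer control, prior-cancer treated, IEN-alone control, IEN-alone treated:

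- HR 0.45: 12.33 + 6.48 + 7.95 + 3.99 ≈ 30.8
- HR 0.40: 12.33 + 5.85 + 7.95 + 3.59 ≈ 29.7

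With 10% loss spread over each patient's own follow-up or over years 0-7, simulation gives about 29.3 to 29.7 and 28.3 to 28.7 events.

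**Simulated power, 40,000 replications per cell.**

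| 10% loss spread over | HR 0.45 | HR 0.40 | Gain (points) |
|---|---|---|---|
| each patient's own follow-up | 78.7% | 85.2% | 6.5 |
| years 0-7 | 79.5% | 86.0% | 6.5 |
| years 0-3 | 78.7% | 84.6% | 5.9 |

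The plan's 79% is reproduced. The 88% is not: the shortfall runs from 88 − 86.0 = 2.0 to 88 − 84.6 = 3.4 points. Separate simulations of the same design gave 78.4 to 79.4% and 84.7 to 85.9%.

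**Chance and rounding.** The standard error for 10,000 replications is √(0.88 × 0.12/10,000) = 0.0033, or 0.33 points. The lowest value that rounds to 88% is 87.5%. That is 1.5 points above the most favourable row, more than four standard errors.

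**Does another setting give both figures?**

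| Departure from the listed assumptions | HR 0.45 | HR 0.40 |
|---|---|---|
| 5% loss | 79.5% | 86.2% |
| no loss | 80.3% | 86.7% |
| no loss and a single look | 81.1% | 87.4% |
| earlier accrual | 80.6% | 87.1% |
| rounded 2-year rates, 10% loss | 79.3-79.7% | 86.3-86.5% |
| rounded 2-year rates, no loss | 80.8% | 87.9% |
| group-sequential Schoenfeld approximation, no loss | 81.7% | 88.2% |

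The single-look Schoenfeld formula, Φ(√(D/4) × |ln HR| − 1.2816), behaves the same way:

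- HR 0.45, D = 29.5: Φ(2.716 × 0.799 − 1.2816) = Φ(0.888) = 0.81
- HR 0.40, D = 28.5: Φ(2.669 × 0.916 − 1.2816) = Φ(1.164) = 0.88

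As these settings bring the second figure close to 88%, they also lift the first above 79%. The gain stays at about 6 to 7 points. The printed pair needs 9, or 8 after the most favourable rounding (79.5 to 87.5).

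**Which hazard ratio gives 88%?** With the listed assumptions unchanged and losses over each patient's own follow-up or years 0-7, power is 87.6 to 88.1% at 0.38 and 88.1 to 88.6% at 0.375.

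**The case against.** Four points can be made for the plan.

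- **The hazard ratio may be rounded.** The alternative is printed as 0.4, to one decimal, while the design value is printed as 0.45. A value of 0.38 rounds to 0.4 and gives about 88% alongside 79%, with no other assumption changed. This stands as a possibility. A reader might infer that no reading yields both figures; that goes too far. Nothing in the documents shows that 0.38 was used, however, and a reader will take 0.4 as 0.40.
- **The inputs are incomplete.** The loss window and accrual pattern are not given, and the simulation code is not part of the documents. This stands, and it is why the shortfall is a range. It does not rescue the figure, because the settings tried that raise power at 0.40 enough to approach 88% raise it at 0.45 too.
- **Some relaxed settings come close to both figures.** Dropping losses gives 80.3% and 86.7%, each within 1.3 points of the printed value. That is closeness rather than reproduction, and it contradicts the stated 10% loss.
- **Nothing depends on the figure.** This also stands. The 104 patients are justified by the power at 0.45; the 88% supports no decision rule, boundary or analysis time.

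**Conclusion.** The 88% is not reproduced from the assumptions listed in section 8.2. Those assumptions give about 85 to 86% at a hazard ratio of 0.40, an overstatement of about 2 to 3.4 points depending on when losses fall. The conclusion rests on uniform accrual, a total loss of 10%, the printed hazards and boundaries, and 0.4 meaning 0.40.

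A reader might infer that the trial is underpowered or its sample size miscalculated. The documents do not support that: the 79% at the design effect is reproduced and the sample size follows from it. Nor is the size of the shortfall fixed to within a few tenths of a point, since the loss window is unstated. This is a minor correction to a secondary statement.

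**What to change.** Rerun the 0.40 case with exactly the assumptions used for the 79%, and restate the power as about 85 to 86%. If 88% came from a different hazard ratio (for example 0.38), print that value to two decimals. If it came from different loss, accrual or boundary assumptions, state them and recompute the 79% under the same ones. In either case, add the accrual pattern and the window for loss times to the assumption list so that both figures can be checked.

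The cost is one simulation run and a sentence or two in section 8.2. The stated power may become slightly less favourable. Sample size, boundaries and analysis times do not change.

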8.3 Statistical Analysis Plan

Patients' demographic and clinical characteristics at baseline will be summarized using descriptive statistics such as frequency distribution, mean (\pm s.d.) and median (range) accompanied by graphical analysis. Student t-test/Wilcoxon test and ANOVA/Kruskal-Wallis test will be used to compare continuous variables between different treatment groups. The chi-square test or the Fisher's exact test will be applied to assess the association between two categorical variables.

A CONSORT diagram will be used to summarize the conduct of the trial.¹⁷

The primary endpoint of the study is oral cancer-free survival defined as time from randomization to the development of histologically confirmed oral cancer or death of any cause, whichever occurs first. For events that have not occurred by the time of data analysis, times will be censored at the last contact at which the patient was known to be oral cancer-free. All patients will be analyzed on an intent-to-treat basis (i.e., as randomized). The distribution of time to oral cancer development will be estimated by the Kaplan-Meier method. Stratified log-rank test¹⁸ will be used to compare cancer-free survival between treatment groups. The Cox (proportional hazards) regression model will be used to incorporate potential prognostic factors and treatment assignment as covariates.

In general, for both the primary endpoint and secondary endpoints, exploratory data analysis and graphical methods will be applied as the first step to examine the distribution of the data, error checking, and outlier identification. Range check and consistency check will be applied to ensure the data quality. Standard distribution plots such as the histogram and box-plot will be applied. A more versatile BLiP plot will be used to facilitate the plotting of both discrete and continuous data. Event charts will be generated to study the relationship between multiple outcomes for time-to-event data at the individual level. Descriptive statistics will be provided to summarize the data. Standard statistical methods for analyzing continuous data, discrete data, and survival data will be applied whenever appropriate.

Toxicity data will be summarized by frequency tables. For the efficacy endpoint, intend-to-treat analysis will be applied to the eligible patients. For the toxicity endpoint, per-treated analysis will be used to include any patient who received the treatment regardless of the eligibility nor the duration or dose of the treatment received.

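### Section 8.3 applies Kaplan-Meier to time to oral cancer, not to the defined endpoint of oral cancer or death; read literally, the endpoint has no specified curve and cancer incidence is overstated

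*Combined protocol and SAP*

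**What the plan says.** Section 8.3 defines the primary endpoint as "oral cancer-free survival defined as time from randomization to the development of histologically confirmed oral cancer or death of any cause, whichever occurs first". Patients without an event are handled by a single rule: "times will be censored at the last contact at which the patient was known to be oral cancer-free". The estimation sentence is "The distribution of time to oral cancer development will be estimated by the Kaplan-Meier method". The next sentence gives the test, a stratified log-rank test that "will be used to compare cancer-free survival between treatment groups". Neither Section 8.2 nor Section 8.3 names a cumulative incidence or competing-risk method.

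Section 8.2 also uses two labels. It bases the sample size on "time from randomization to onset of oral cancer or death", but assumption 3 of the list that follows reads "Time-to-oral cancer development follows an exponential distribution". Assumption 4 expresses the effect as a reduction in the 2-year oral cancer rate. Assumption 5 counts competing risk within the 10% loss to follow-up.

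**The concern.** The definition and the test refer to a composite in which death is an event. The sentence between them, the only one that specifies a survival curve, refers to oral cancer alone. A programmer who follows it literally has to do something with patients who die without oral cancer, and the usual step is to censor them. Two things then go wrong.

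- The primary endpoint as defined has no specified curve or event-free estimate by arm.
- One minus Kaplan-Meier, read as the probability of developing oral cancer, is too high, because patients who have died are treated as if they could still develop it.

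In a prevention trial, oral cancer risk by arm and the difference between arms are figures that readers will look for and that a later trial may be planned on. The point therefore matters for description and planning, though not for the primary test.

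**Working it through.** **Inputs from Section 8.2.** The exponential rates per year "are 0.1179 (control) and 0.053 (treatment) in IEN/LOH-cancer history patients and 0.0813 (control) and 0.0366 (treatment) in IEN/LOH-alone patients"; 56 patients with prior cancer and 48 with IEN alone; 4 years of accrual and 3 further years of follow-up; 10% loss to follow-up.

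**Input not in the documents.** The rate of death without oral cancer, d. Assumed range: 1% to 5% per year, equal in both arms unless stated otherwise.

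**Step 1: reproduce the plan's own figures.** The control rates follow from the 2-year oral cancer rates: −ln(1 − 0.21)/2 = 0.1179 and −ln(1 − 0.15)/2 = 0.0813. A simulation with 10,000 replications used the stated rates, boundaries and two strata, with uniform accrual and 10% lost at a uniform time. It generated oral cancer events only and gave 79.1% power against the stated 79%. So the stated power is consistent with a design model that counts no deaths as events. This is supporting evidence only: the companion figure, 88% at a hazard ratio of 0.40, came out at 85.4% under the same set-up.

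**Step 2: one rate per arm.** Weighting by stratum size:

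- control: c = (56 × 0.1179 + 48 × 0.0813)/104 = 0.101 per year
- pembrolizumab: 0.45 × 0.101 = 0.0455 per year

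**Step 3: formulas under constant hazards.**

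- One minus Kaplan-Meier with deaths censored: 1 − exp(−c·t)
- Cumulative incidence of oral cancer: c/(c + d) × [1 − exp(−(c + d)·t)]
- Risk of the defined endpoint (cancer or death): 1 − exp(−(c + d)·t)

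**Step 4: worked example.** Control arm, t = 5, d = 0.05. One minus Kaplan-Meier is 1 − exp(−0.505) = 39.6%. Cumulative incidence is (0.101/0.151) × [1 − exp(−0.755)] = 0.669 × 0.530 = 35.4%. The excess is 4.2 points.

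**Step 5: results for d from 1% to 5% per year.**

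| Quantity | 3 years | 5 years |
|---|---|---|
| Control, 1 − KM, deaths censored | 26.1% | 39.6% |
| Control, cumulative incidence | 25.8% to 24.4% | 38.8% to 35.4% |
| Control excess (points) | 0.4 to 1.8 | 0.9 to 4.2 |
| Pembrolizumab excess (points) | 0.2 to 0.9 | 0.5 to 2.3 |
| Overstatement of absolute reduction (points) | 0.2 to 0.9 | 0.4 to 1.9 |
| Control, risk of cancer or death | 28.3% to 36.4% | 42.6% to 53.0% |

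The last row shows the other side of the mismatch. Offered as a description of the defined endpoint, a cancer-only curve would understate the control-arm risk by about 2 to 10 points at 3 years and 3 to 13 points at 5 years.

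**Step 6: unequal death rates.** Take d = 1% per year in control and 3% on pembrolizumab. At 5 years the excess is 0.9 points in control and 1.4 points on pembrolizumab, so the absolute reduction is understated by about 0.5 points. The direction of the error in the difference therefore depends on the death rates.

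**Step 7: composite reading.** If death counts as an event in the curve, no competing event remains and this bias is zero.

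**The case against.** A reader might infer that Section 8.3 commits the trial to a biased analysis, and that the reported oral cancer risk and the benefit will both be inflated. The documents do not support that, for four reasons.

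- **The text does not censor deaths.** The sentence stands between a composite definition and a composite test, and the single censoring rule is for events that have not occurred. It may simply be a loose label for oral cancer-free survival, in which case Kaplan-Meier is the correct estimator. This stands, and it makes the bias conditional. It does not settle the reading, because Section 8.2 models time to oral cancer and places competing risk in loss to follow-up, which is how a cancer-only analysis with deaths censored would be set up.
- **The size depends on an assumed death rate and a long horizon.** The nearest figure in the plan is the 10% loss from all causes. If all of it were deaths over about 5 years (3 years plus half of the 4-year accrual), the rate would be −ln(0.9)/5 = 2.1% per year. At 2% the control excess is 0.7 points at 3 years and 1.8 at 5, and the overstatement of the reduction is 0.4 and 0.8. A rate of 5% implies 1 − exp(−0.25) = 22% dying over 5 years in the absence of cancer. The upper end of the range is therefore far above what the plan allows for. With 52 patients per arm, the binomial standard error of the difference, before censoring, is about 7.7 points at 3 years and 8.8 at 5, well above the bias.
- **The direction is not fixed.** Inflation of the benefit needs similar death rates in both arms; Step 6 gives a case where it reverses.
- **The primary decision does not use the curve.** The stratified log-rank test is specified on cancer-free survival. This stands in full.

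What remains is that the one estimation sentence does not name the endpoint, and that one of its two readings gives a wrong estimate of cancer incidence.

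**Conclusion.** The mismatch is real and should be corrected; the bias is conditional. Read literally with deaths censored, the plan has no curve for the defined endpoint. Its cancer incidence in controls is too high by about 0.4 to 1.8 points at 3 years and 0.9 to 4.2 at 5 years, and the absolute reduction is overstated by about 0.2 to 0.9 and 0.4 to 2 points. These figures rest on constant hazards, the design rates in Section 8.2 averaged over strata, and an assumed rate of death without oral cancer of 1% to 5% per year that is equal in the two arms. Read as the composite, the sentence only names the wrong variable and the bias is zero; oral cancer incidence alone then has no specified estimator. Neither reading touches the primary test. It would go too far to say that the trial's reported cancer risk will be biased, or that its benefit will be exaggerated.

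**What to change.** In Section 8.3, replace the estimation sentence with two statements:

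1. Oral cancer-free survival (oral cancer or death of any cause) is estimated by Kaplan-Meier for each arm.
2. Any incidence reported for oral cancer alone is estimated by the Aalen-Johansen cumulative incidence function, with death without oral cancer as the competing event.

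A stratified cause-specific hazard ratio for oral cancer could be added as a supportive analysis, but it is optional in a trial of 104 patients where about 29 oral cancer events are expected (simulated mean under the design assumptions).

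The cost is a few sentences and a little programming. No new data are needed, because the primary endpoint already requires both cancer and death to be recorded.
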